7.2.3 Evaluating Adverse Events

An investigator who is a qualified physician will evaluate all adverse events with respect to the elements outlined in [Table 2](#). The investigator's assessment of causality is required for each adverse event. Refer to [Table 2](#) for instructions in evaluating adverse events.

Table 2 Evaluating Adverse Events

Maximum Intensity	Mild	awareness of sign or symptom, but easily tolerated (for pediatric trials, awareness of symptom, but easily tolerated)
	Moderate	discomfort enough to cause interference with usual activity (for pediatric trials, definitely acting like something is wrong)
	Severe	incapacitating with inability to work or do usual activity (for pediatric trials, extremely distressed or unable to do usual activities) Injection site redness or swelling from the day of vaccination through Day 5 post-vaccination will be evaluated by maximum size.
Seriousness	A serious adverse event (AE) is any adverse event occurring at any dose that:	
	† Results in death; or	
	† Is life threatening; or places the subject, in the view of the investigator, at immediate risk of death from the event as it occurred [Note: This does not include an adverse event that, had it occurred in a more severe form, might have caused death.]; or	
	† Results in a persistent or significant disability/incapacity (substantial disruption of one's ability to conduct normal life functions); or	
	† Results in or prolongs an existing inpatient hospitalization (hospitalization is defined as an inpatient admission, regardless of length of stay, even if the hospitalization is a precautionary measure for continued observation. (Note: Hospitalization for an elective procedure to treat a pre-existing condition that has not worsened is not a serious adverse event. A pre-existing condition is a clinical condition that is diagnosed prior to the use of a Merck product and is documented in the patient's medical history.); or	
	† Is a congenital anomaly/birth defect (in offspring of subject taking the product regardless of time to diagnosis); or	
	Is a cancer (although not serious per ICH definition, is reportable to the Sponsor within 24 hours to meet certain local requirements; or	
	Overdose , although not serious per ICH definition, whether accidental or intentional, with or without an accompanying adverse event/serious adverse event, is reportable to the Sponsor within 24 hours to meet certain local requirements. Other important medical events that may not result in death, not be life threatening, or not require hospitalization may be considered a serious adverse event when, based upon appropriate medical judgment, the event may jeopardize the subject and may require medical or surgical intervention to prevent one of the outcomes listed previously (designated above by a †).	
Duration	Record the start and stop dates of the adverse event. If less than 1 day, indicate the appropriate length of time and units	
Action taken	Did the adverse event cause the test vaccine to be discontinued?	
Relationship to test vaccine	Did the test vaccine cause the adverse event? The determination of the likelihood that the test vaccine caused the adverse event will be provided by an investigator who is a qualified physician. The investigator's signed/dated initials on the source document or worksheet that supports the causality noted on the AE form, ensures that a medically qualified assessment of causality was done. This initialed document must be retained for the required regulatory time frame. The criteria below are intended as reference guidelines to assist the investigator in assessing the likelihood of a relationship between the test vaccine and the adverse event based upon the available information. The following components are to be used to assess the relationship between the test vaccine and the AE; the greater the correlation with the components and their respective elements (in number and/or intensity), the more likely the test vaccine caused the adverse event:	
	Exposure	Is there evidence that the subject was actually exposed to the test vaccine such as: reliable history, acceptable compliance assessment (e.g., diary), seroconversion or identification of vaccine virus in bodily specimen?
	Time Course	Did the AE follow in a reasonable temporal sequence from administration of the test vaccine? Is the time of onset of the AE compatible with a vaccine-induced effect?
	Likely Cause	Is the AE not reasonably explained by another etiology such as underlying disease, other drug(s)/vaccine(s), or other host or environmental factors

Relationship to test vaccine (continued)	The following components are to be used to assess the relationship between the test vaccine and the AE: (continued)	
	Dechallenge	(not applicable for vaccines)
	Rechallenge	
Was the subject reexposed to the test vaccine in this trial? If yes, did the AE recur or worsen? If yes, this is a positive rechallenge. If no, this is a negative rechallenge. (Note: This criterion is not applicable if: (1) the initial AE resulted in death or permanent disability, or (2) the trial is a single-dose vaccine trial.) NOTE: IF A RECHALLENGE IS PLANNED FOR AN ADVERSE EVENT WHICH WAS SERIOUS AND WHICH MAY HAVE BEEN CAUSED BY THE TEST VACCINE, OR IF REEXPOSURE TO THE TEST VACCINE POSES ADDITIONAL POTENTIAL SIGNIFICANT RISK TO THE SUBJECT, THEN THE RECHALLENGE MUST BE APPROVED IN ADVANCE BY THE SPONSOR CLINICAL DIRECTOR AND THE INSTITUTIONAL REVIEW BOARD/INDEPENDENT ETHICS COMMITTEE.

Consistency with Trial Vaccine Profile	Is the clinical/pathological presentation of the AE consistent with previous knowledge regarding the test vaccine or vaccine class pharmacology or toxicology?	
The assessment of relationship will be reported on the case report forms /worksheets by an investigator who is a qualified physician according to his/her best clinical judgment, including consideration of the above elements.		
Record one of the following:	Use the following criteria as guidance (not all criteria must be present to be indicative of a vaccine relationship).	
Yes, there is a reasonable possibility of vaccine relationship.	There is evidence of exposure to the test vaccine. The temporal sequence of the AE onset relative to the administration of the test vaccine is reasonable. The AE is more likely explained by the test vaccine than by another cause.	
No, there is not a reasonable possibility of vaccine relationship	Subject did not receive the test vaccine OR temporal sequence of the AE onset relative to administration of the test vaccine is not reasonable OR the AE is more likely explained by another cause than the Sponsor's product. (Also entered for a subject with overdose without an associated AE.)	

7.2.4 Sponsor Responsibility for Reporting Adverse Events

All Adverse Events will be reported to regulatory authorities, IRB/IECs and investigators in accordance with all applicable global laws and regulations, i.e., per ICH Topic E6 (R1) Guidelines for Good Clinical Practice.

8.0 STATISTICAL ANALYSIS PLAN

This section outlines the statistical analysis strategy and procedures for the study. Changes to analyses made after the protocol has been finalized, but prior to final database lock, will be documented in a supplemental SAP (sSAP) and referenced in the Clinical Study Report (CSR) for the study. Post hoc exploratory analyses will be clearly identified in the CSR.

The immunogenicity and safety analysis of Day 1 through Month 7 will be performed after the data through Month 7 have been declared final and complete. The analysis of Month 18 through Month 30 immunogenicity and safety data will take place at the end of the study. The results of this study will be summarized in 2 separate reports. The first report is the CSR including the immunogenicity and safety results based on the data through Month 7. The second one is an update to the CSR, including persistence of immune response and safety results through the end of the study.

8.1 Statistical Analysis Plan Summary

Key elements of the statistical analysis plan are summarized below; the comprehensive plan is provided in Sections 8.2-8.12.

Study Design Overview	A phase III, open-label, clinical trial to study the safety and immunogenicity of the quadrivalent HPV (Types 6, 11, 16, 18) L1 VLP Particle (VLP) vaccine in 9- to 15-year-old boy
Treatment Assignment	Subjects meeting inclusion/exclusion criteria will be allocated to V501.
Analysis Populations	Immunogenicity: Per-Protocol Immunogenicity (PPI) Safety: All Subjects as Treated (ASaT)
Primary Endpoint(s)	Primary immunogenicity endpoint will be seroconversion rate for the vaccine HPV types (6, 11, 16 and 18) at 4 weeks post dose 3.
Key Secondary Endpoints	Key secondary endpoint includes cLIA geometric mean titers (GMTs) for the vaccine HPV type (6, 11, 16 and 18) at 4 weeks post dose 3.
Statistical Methods for Key Efficacy/Immunogenicity/ Pharmacokinetic Analyses	The primary hypothesis with respect to anti-HPV 6, 11, 16 and 18 seroconversion percentages by 4 weeks post dose 3 will be evaluated by computing point estimates and constructing 95% confidence interval. (The success criterion for the primary analysis requires that point estimates for seroconversion rate be greater than 90% for all 4 vaccine HPV types.) The secondary hypothesis will be evaluated by comparing anti-HPV 6, 11, 16 and 18 GMTs at 4 weeks post dose 3 in 9- to 15-year-old boys from this study with those in 16- to 26-year old young men (all young men who were vaccinated by V501 and met the per-protocol immunogenicity criteria of PN122 will be included) by constructing a 95% confidence interval for the ratio of GMTs.

Statistical Methods for Key Safety Analyses	The adverse experiences of interest in this study include injection site adverse experiences/vaccine-related adverse experiences prompted for on the VRC occurring Day 1 through Day 5 following any vaccination, systemic adverse experiences/vaccine-related adverse experiences reported Day 1 through Day 15, elevated temperatures from Day 1 to Day 5 following any vaccination. Summary tables will be provided.
Interim Analyses	The immunogenicity and safety analysis of Day 1 through Month 7 will be performed after the data through Month 7 have been declared final and complete. The analysis of Month 18 through Month 30 immunogenicity and safety data will take place at the end of the study.
Multiplicity	For the primary hypothesis, no multiplicity adjustment is required since success requires the observed seroconversion rates for all 4 vaccine HPV types to be greater than 90%. Similarly, for the secondary hypothesis for comparing GMTs between 9- to 15-year-old boys and 16- to 26-year old young men, success is required on all 4 vaccine HPV types. Therefore, no multiplicity adjustment will be made to account for the multiple HPV types. The secondary hypothesis will only be tested if the primary hypothesis is demonstrated successfully.
Sample Size and Power	This study will enroll 100 subjects to receive V501, and will allow estimation of seroconversion percentage with a 95% confidence interval with a half-width of approximately 5 percentage points to assess the primary objective. Given the true seroconversion percentage of 95%, there is 92% probability that the point estimates are greater than 90% for all 4 vaccine HPV types. This is based on the assumption of an approximately 5% dropout and/or protocol violation rate. For the secondary hypothesis, a sample size of 95 boys from this study and 400 young men from PN122 has more than 99% probability that the lower bounds of 95%CI exceed 0.5 for all 4 HPV types given the underlying true GMT ratio is 1.0. This is based on the following assumptions for young men from PN122 in addition to that for boys described above: no general protocol violation of 95%; exclusion rate due to Day 1 seropositive or PCR positive between Day 1 and Month 7 to HPV 6, 11, 16, and 18 is approximately 15%; 90% of randomized subjects completed vaccination phase.

8.2 RESPONSIBILITY FOR ANALYSES/IN-HOUSE BLINDING

The statistical analysis of the data obtained from this study will be the responsibility of the designee/Clinical Biostatistics department of the SPONSOR. This trial is being conducted as a non-randomized, open-label study, i.e., subjects, investigators, and SPONSOR personnel will be aware of subject treatment assignments after each subject is enrolled and treatment is assigned.

8.3 HYPOTHESES/ESTIMATION

Objectives and hypotheses of the study are stated in Section 3.1.

8.4 ANALAYSIS ENDPOINTS

Immunogenicity and safety endpoints that will be evaluated for within- and/or between-age group differences are listed below, followed by the descriptions of the derivations of selected endpoints.

8.4.1 Immunogenicity Endpoints

The primary immunogenicity endpoints are seroconversion percentages to HPV 6, 11, 16 and 18 by 4 weeks post dose 3. Seroconversion is defined as changing serostatus from seronegative to seropositive. A subject with a competitive Luminex Immunoassay (cLIA) titer at or above the serostatus cutoff for a given HPV type is considered seropositive for that HPV type. The key secondary immunogenicity endpoints include cLIA geometric mean titers (GMTs) to HPV 6, 11, 16 and 18 at 4 weeks post dose 3. Other secondary endpoints include both cLIA GMTs and seroconversion percentages for each vaccine HPV type at Months 18 and 30 to assess persistence of immune responses.

8.4.2 Safety Endpoints

Safety assessment will focus on the injection site adverse experiences/vaccine-related adverse experiences and elevated temperatures on Days 1 to 5 post-vaccination, and systemic adverse experiences/vaccine-related systemic adverse experiences on Days 1 to 15 post-vaccination, reported on the Vaccination Report Card (VRC). Serious adverse experiences reported Days 1 to 15 post-vaccination, vaccine-related serious adverse experiences reported any time during the study and new medical condition occurring any time during the study will also be summarized.

8.5 ANALYSIS POPULATION

8.5.1 Immunogenicity Analysis Populations

Per Protocol Immunogenicity (PPI) Population

The Per Protocol Immunogenicity (PPI) population will serve as the primary population for the analysis of immune response to each of the 4 HPV types (6, 11, 16 and 18). To be included in this population, subjects must:

- (1) Have received all 3 vaccinations with the correct dose of the correct clinical material, and each vaccination visit must occur within acceptable day ranges (See [Table 3](#) for acceptable day ranges for vaccination visits).
- (2) Have provided Month 7 serology result within 21 to 49 days post dose 3.
- (3) Be seronegative to the appropriate HPV type at Day 1 (See [Table 4](#) for acceptable day ranges for serum samples at Day 1).
- (4) Have no other protocol violations that could interfere with the evaluation of subject's immune response to the study vaccine.

To be included in the PPI population for HPV 6 or 11, subjects must be seronegative to both HPV 6 and 11 at Day 1. To be included in the PPI population for any other vaccine HPV type, subjects need to be seronegative at Day 1 only for the HPV type being analyzed. The final determination on protocol violations, which will be used for determining the Per-Protocol Immunogenicity population, will be made prior to the database lock and will be documented in a separate memo.

Table 3 Acceptable Day Ranges for Vaccination Visits

Dose of 4-Valent HPV L1 VLP Vaccine Scheduled for Injection	Protocol Specified Visit Window	Day Range for Inclusion in Statistical Analysis (Relative to Day 1 [†])
Dose 1	Day 1 [†]	0
Dose 2	Month 2 ± 3 weeks	36 to 84
Dose 3	Month 6 ± 4 weeks	148 to 218
[†] Day 1 refers to the date when dose 1 of 4-valent HPV L1 VLP vaccine is injected.		

Table 4 Acceptable Day Ranges for Collection of Serum Samples

Study Visit	Sample Type	Target Collection Day (Relative to Day 1 [†])	Day Range for Inclusion in Statistical Analysis (Relative to Day 1) [†]
Day 1	Serum	0	-14 to 0
Month 7	Serum	30 days post dose 3	21 to 49 post dose 3
Month 18	Serum	548	366 to 730
Month 30	Serum	913	731 to 1004
[†] Day 1 refers to the date when dose 1 of 4-valent HPV L1 VLP vaccine is injected. For Month 7, indicated target collection/day range is relative to date of injection of dose 3 of 4-valent HPV L1 VLP vaccine.			

All Type-Specific Naïve Subjects with Serology (ANSS) Population

A supportive immunogenicity analysis will be carried out on the all type-specific naïve subjects with serology population. To be included in this population, subjects must:

- (1) Have received all 3 vaccinations
- (2) Have provided post dose 3 serology data
- (3) Be seronegative to the appropriate HPV type at Day 1

To be included in the ANSS population for HPV 6 or 11, subjects must be seronegative to both HPV 6 and 11 at Day 1. To be included in the ANSS population for any other vaccine HPV type, subjects need to be seronegative at Day 1 only for the HPV type being analyzed. Unlike the PPI population, this population will include general protocol

violators. In addition, no ranges on the timing of the vaccination will be applied. Acceptable day ranges for serum samples at Day 1 will be the same as in the PPI population. Acceptable day range for serum samples at Month 7 will be broader than in the PPI population, extending from Day 1 post dose 3 to Day 105 post dose 3.

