5.1.3 Subject Exclusion Criteria

The subject must be excluded from participating in the trial if the subject:

1. Is concurrently enrolled in clinical studies of investigational agents
2. Has history of known prior vaccination with an HPV vaccine or plans to receive the HPV vaccine outside of the study.
3. Has receipt of inactivated vaccines within 14 days prior to enrollment or receipt of live virus vaccines within 28 days prior to enrollment. If the subject meets this criterion, the Day 1 visit will be rescheduled for a time when this criterion is not met.
4. Has history of severe allergic reaction (e.g., swelling of the mouth and throat, difficulty breathing, hypotension or shock) that required medical intervention.
5. Is allergic to any vaccine component, including aluminum, yeast, or BENZONASE™ (nuclease, Nycomed [used to remove residual nucleic acids from this and other vaccines]).
6. Has received any immune globulin or blood derived products within the 6 months prior to the first injection, or plan to receive any through Month 7 of the study.
7. Has history of splenectomy or is currently immunocompromised or has been diagnosed as having a congenital or acquired immunodeficiency, HIV infection, lymphoma, leukemia, systemic lupus erythematosus (SLE), rheumatoid arthritis, juvenile rheumatoid arthritis (JRA), inflammatory bowel disease, or other auto immune condition.
8. Is receiving, or has received in the year prior to enrollment the following immunosuppressive therapies: radiation therapy, cyclophosphamide, azathioprine, methotrexate, any chemotherapy, cyclosporin, leflunomide, TNF- α antagonists, monoclonal antibody therapies (including rituximab), intravenous gamma globulin, antilymphocyte sera, or other therapy known to interfere with the immune response. With regard to systemic corticosteroids, a subject will be excluded if he is currently receiving steroid therapy, has recently (defined as within 2 weeks of enrollment) received such therapy, or has received 2 or more courses of high dose corticosteroids

(orally or parenterally) lasting at least 1 week in duration in the year prior to enrollment. Subjects using inhaled, nasal, or topical corticosteroids are considered eligible for the study.

9. Has known thrombocytopenia or any coagulation disorder that would contraindicate intramuscular injections.

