5.5 Concomitant Medications/Vaccinations (Allowed & Prohibited)

See the exclusion criteria for specific restrictions for prior and concomitant medications at Day 1.

To reduce their potential interference with the evaluation of the immunologic response and reactogenicity of the study vaccine, non-study inactivated vaccines must not be administered within the 14 days before or 14 days after any dose of study vaccine. Non-study live virus vaccines must not be administered within the 28 days prior to or 14 days after any dose of study vaccine. Non-study HPV vaccine must not be used at any time during the study. Immune globulin or blood-derived products must not be administered within 6 months prior to vaccination through Month 7. Systemic corticosteroids should not be administered within 2 weeks prior to vaccination through Month 7, if at all possible. Subjects may receive allergen desensitization therapy and tuberculin skin testing while participating in the study.

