7.1.1.5.2 Concomitant Medications

The investigator or qualified designee will record medication, if any, taken by the subject during the trial.

Use of medicines and non-study vaccines should be documented in the data collection system in the following manner:

- Medications (corticosteroids, immunosuppressives, immune globulins, and blood products) from 3 days prior to Day 1 through Month 7;
- Medications from 3 days prior to each study vaccination through 14 days after each study vaccination;
- Non-Replicating (Inactive) Vaccines for 14 days prior to each study vaccination through 14 days after each study vaccination; and
- Replicating (Live) Vaccines for 28 days prior to each study vaccination through 14 days after each study vaccination.
- Non-study HPV vaccine must not be used at any time during the study. However, for the specific case where a subject mistakenly receives any non-study HPV vaccines, the nonstudy HPV vaccine must be reported on the appropriate eCRF, regardless of when the non-study vaccine was received.

Please refer to the eCRF Entry Guidelines for further details.

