7.1.5.1 Prerequisites for Study Vaccination Visit

See the inclusion/exclusion criteria for specific restrictions at Visit 1 (Day 1). For visits with study vaccination (Visit 1, 2 and 3), study personnel should verify by questioning the subject and/or by examination that:

- The subject has not had a fever (define as an oral temperature of $\geq 37.5^{\circ}\text{C}$) within 24-hour period prior to any study vaccination visit.
- The subject has not received any systemic (oral or parenteral) corticosteroids in the 2 weeks prior to any study vaccination visit.
- The subject has not received a non-study inactive vaccine within 14 days prior to any study vaccination visit or a non-study live vaccine within 28 days prior to any study vaccination visit.

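### Does the open-ended protocol-violation criterion for the per-protocol population let Month 7 titers decide who is analysed?

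*Combined protocol and SAP*

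**What the plan says.** Section 8.5.1 admits a boy to the PPI population if he had all three correct doses within the day ranges, gave a Month 7 sample 21 to 49 days after dose 3, was seronegative at Day 1 for the relevant type, and met a fourth condition: "Have no other protocol violations that could interfere with the evaluation of subject's immune response to the study vaccine". The timing rule is: "The final determination on protocol violations, which will be used for determining the Per-Protocol Immunogenicity population, will be made prior to the database lock". The same sentence requires a separate memo.

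Other sections show which exposures the authors had in mind. Section 5.5 restricts non-study vaccines, immune globulin, blood products and corticosteroids, with the stated purpose "To reduce their potential interference with the evaluation of the immunologic response and reactogenicity of the study vaccine". It adds "Non-study HPV vaccine must not be used at any time during the study". Section 5.1.3, item 6, excludes a boy who "Has received any immune globulin or blood derived products within the 6 months prior to the first injection". Section 7.1.1.5.2 requires recording of "Medications (corticosteroids, immunosuppressives, immune globulins, and blood products) from 3 days prior to Day 1 through Month 7".

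Section 8.5.1 also defines a supportive population, all type-specific naïve subjects with serology (ANSS), which keeps general protocol violators. Table 5 applies it to the seroconversion and GMT estimates, but not to the GMT ratio against the men of Protocol 122.

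**The concern.** The fourth criterion is the only one that cannot be applied mechanically. The lists in sections 5.1.3, 5.5 and 7.1.5.1 say what to avoid or check; they do not say which departures remove a boy from the PPI population. Corticosteroids show the difficulty. Section 5.5 says "Systemic corticosteroids should not be administered within 2 weeks prior to vaccination through Month 7, if at all possible", while section 7.1.5.1 has staff verify that "The subject has not received any systemic (oral or parenteral) corticosteroids in the 2 weeks prior to any study vaccination visit". The PPI consequence of a course outside those two weeks but before Month 7 is not stated.

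The trial is open-label with one group, and the sponsor both receives the serology and analyses it. A Month 7 titer alone shows which way an exclusion would push the result, so a decision made before lock could still be made with the outcome in view. Two analyses are planned, and section 8.0 describes the first cut only as data declared final and complete, so it is also unclear which lock is meant.

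At stake is the primary conclusion, which has no confidence-limit requirement. Under section 8.8 the GMT non-inferiority test is opened only by primary success.

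**Working it through.** **Inputs.** From section 8.9.1: 95 evaluable boys; planning rate 95%; reference rates in Japanese girls (PN028) of 97.5%, 98.8%, 98.8% and 98.8% for types 6, 11, 16 and 18. From section 8.6.1: success if the point estimate exceeds 90% for every type. From section 8.9.2: 95 boys, 400 men, SD 1.2 on the natural-log scale, margin 0.5, one-sided alpha 0.025. Independence across types is assumed; multiplying on that basis reproduces Table 7.

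**The plan's own figures.** The smallest passing count is 86, since 86/95 = 90.5% and 85/95 = 89.5%. At 95%, P(X ≥ 86) = 0.9795 per type and 0.9795⁴ = 0.920 for all four. Table 7 gives 0.98 and 0.92. The chance of failing is 1 − 0.920 = 8.0%.

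**Where an exclusion can change the answer.** With one non-responder dropped, 85/95 becomes 85/94 = 90.4%. With two dropped, 84/95 = 88.4% becomes 84/93 = 90.3%. Dropping a boy who responded to another type does no harm at the boundary there, because 86/95 becomes 85/94, still a pass.

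**How often the counts lie there.**

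- Exactly one type at 85 and the other three passing, at 95%: 4 × P(X = 85) × P(X ≥ 86)³ = 4 × 0.01261 × 0.97947³ = 4.74%.
- Up to one non-responder dropped per type: P(X ≥ 85)⁴ − P(X ≥ 86)⁴ = 0.9687 − 0.9204 = 4.8%.
- Up to two per type: P(X ≥ 84)⁴ − P(X ≥ 86)⁴ = 0.9889 − 0.9204 = 6.9%. The ceiling for any number is the 8.0% chance of failing.
- At the PN028 rates, the failure chance is 0.0140%; one drop per type could rescue 0.0113% and two 0.0135%.
- At a true 99%, the one-drop figure is about 0.00002%.

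**The non-responder must also have an arguable violation.** The documents do not say how many boys will, so assume k of the 95, unrelated to response. With 10 non-responders, the chance of at least one overlap is 1 − C(85,k)/C(95,k):

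| k | Overlap | × 4.74% (true 95%) | × 0.0113% (PN028) |
|---|---|---|---|
| 1 | 0.105 | 0.50% | 0.0012% |
| 3 | 0.286 | 1.36% | 0.0032% |
| 5 | 0.434 | 2.06% | 0.0049% |

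These products cover the single-exclusion route. They still leave out the chance that anyone looks at the titers and acts on them.

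**GMT ratio.** In 40,000 simulated trials at a true ratio of 1.0, power per type was 0.999 with nobody dropped and 0.9998 after dropping the three lowest boys' titers. At a true ratio of exactly 0.5, dropping the lowest one, two or three raised the one-sided error per type from about 0.025 to 0.044, 0.066 and 0.093. Those are worst cases, in which the lowest titers always belong to boys with an arguable violation.

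**The case for a change.** The best case for a change is that it would cost one sentence. Good practice is to settle per-protocol membership without sight of the outcome, and a memo records a decision without making it independent of the titers.

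ANSS is also an imperfect check. It has no success criterion. It drops the vaccination windows and accepts Month 7 samples from Day 1 to Day 105 after dose 3, so a difference from the PPI result would not by itself point to the fourth criterion. It does not cover the GMT ratio, which is the bridging comparison, and there the error inflation at the margin is not trivial.

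All of this is accurate as description, and a sponsor who wanted to tie the memo to the release of Month 7 titers could reasonably do so. It does not show that the plan as written leads to a wrong conclusion. The GMT inflation arises only if boys truly respond half as strongly as men, whereas the sample-size section works with ratios of 1.0 and 1.5. ANSS would still show a primary result that depended on excluding violators. The silence is in this document only: section 10.6 says that data-management procedures are provided separately, and those would be a natural place for a rule on who sees serology and when. A closed list of qualifying violations also has a cost. It could miss an interfering departure that nobody foresaw, or one from before Month 7 that is found late. The open wording of the fourth criterion handles both.

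**Conclusion.** No change follows. The plan leaves unsaid who may see Month 7 titers when violations are judged, and which violations count. It does fix the essentials: a determination before lock, a written record, and a supportive analysis of the primary endpoint that keeps the violators. Because the Month 7 report needs a PPI population, the sensible reading is that the determination is complete before that first analysis. The exposures likely to matter are already named and recorded.

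The size supports this. At the PN028 rates, the chance that a single arguable exclusion could turn the primary result is 0.0012% to 0.0049%. At the 95% planning rate, which the plan sets below its own expectation of about 100%, it is 0.5% to 2.1%. These figures assume 95 evaluable boys, independence across types, and 1 to 5 arguable violators unrelated to response. The last is an assumption, not a figure from the documents. The concern would carry weight only if true seroconversion were near 90% or the true GMT ratio near 0.5, and nothing in the documents suggests either.
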